- 34) Are there any potential direct benefits to individual subjects related to the research?
 YES NO

IF YES, please explain (address whether these benefits (e.g., clinical, therapeutic) would be available to subjects outside of the research):

RESPONSE:

- 35) Explain the potential benefits to science, and/or society (indirect benefits) which may accrue as a result of this research:

RESPONSE: Antibiotic resistance is growing in the world, and this study may provide prospective, randomized data that antibiotics do not result in a benefit to patients. Hopefully surgeons would stop giving postoperative antibiotics, and decrease the risk of side-effects from antibiotics (allergic reactions, clostridium difficile infection, GI upset, etc) to future patients. Also health care costs would be decreased by reducing antibiotic prescriptions.

- 36) If more than minimal risk, address how risks relate to benefits:

RESPONSE: While not “minimal risk”, the risk to patients is low, as detailed above. Many patients have adverse reactions to antibiotics, and if this study shows that the outcomes of patients undergoing sinus surgery without antibiotics are not worse, then hopefully less patients will be prescribed antibiotics.

CONSENT PROCESS

- 37) Describe the consent process in detail. Include who specifically will be obtaining consent, describe their knowledge/experience in obtaining consent from research subjects, and include the location where study information will be exchanged, how (consent form, orally, information sheet, etc.) information is being conveyed to subjects, and when the consent will be obtained (e.g. during pre-surgical visit, about one week before the screening visit):

RESPONSE: Consent will be obtained by [name], [name] or [name] in the clinic during the subject's preoperative visit in the MEEI sinus center. There is a formal consent form that is signed by patients and an oral script (these are on IRBNET). Subjects can think about the study and opt out of randomization at the time of surgery (usually 2-4 weeks elapse between preoperative visit and surgery).

- 38) Indicate which of the following consent procedures you are contemplating for this research:

Written consent form

- Short form process (only appropriate for minimal risk studies)
** If checked, answer question 42 below.*
- Assent from adults with diminished decision-making capacity
**If checked, provide justification below:*
- Assent from children and parental permission

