- Oral consent or implied consent (e.g. completing a survey)
**If checked, provide justification based on [45 CFR 46.117\(c\)](#) below:*
- Requesting a waiver of informed consent from the HSC
**If checked, provide justification based on [45 CFR 46.116\(c\) and \(d\)](#) below:*

RESPONSE:

- 39)** Describe any foreseeable circumstances and/or reasons under which the subject's participation in the research may be terminated:

RESPONSE: If the patient does not want to participate further then they may opt out at any time during the study.

- 40)** How is subject comprehension assessed initially and throughout the consent process? Is the manner in which information is presented appropriate for the population? In cases where subject comprehension is severely limited what special provisions have been made (is there a third party involved in the consent process)? Discuss below:

RESPONSE: The investigators will describe the study according to the oral script and ask the patient if they understand everything that has been explained to them. We will ask them if they have any questions and answer them to their satisfaction. If the patients' comprehension is severely limited then we will not include them in the study.

- 41)** If the research-related intervention or interaction will occur on the same day that the subject initially receives information about the study, justify why this is appropriate/necessary:

RESPONSE: It will not be on the same day, patients will be enrolled at their post operative visit.

- 42)** Describe additional provisions in place for non-English speaking subjects (view [guidance](#)), including the availability/presence of translators (fluent in both English and the subject's spoken language) during the consent process and the translation of consent documents in a language understandable to them (when consent documents are translated all translated versions must be accompanied by an attestation from the translator) **OR** justify why non-English speaking subject are being excluded from the research:

RESPONSE: We would like to apply for use of the short form consent process for patients that do not speak English. We have used translators for patients that are not English speakers previously.

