### **Statistical Analysis Plan**

The primary endpoint was the overall change in SNOT-22 scores from baseline to the final study visit. Secondary outcomes included the change in LK Endoscopic Score from the same time points, as well as rates of post-operative infection. Additional exploratory analyses included the effect of baseline clinical factors, including baseline sinus culture results, history of prior sinus surgery, comorbid asthma, and presence of nasal polyps.

The primary outcome and secondary outcome were analyzed using a repeated-measures analysis of variance (ANOVA) to assess for a group x time interaction on clinical scores. For the secondary analysis of the primary outcome, this model was modified to include baseline clinical covariates in a repeated-measures analysis of covariance (ANCOVA).

The achieved power for non-inferiority was calculated via the same methods as the prospective power analysis. Rather than an *a priori* estimate of standard deviation in scores, the achieved power was based on the actual number of randomized subjects and the actual pooled standard deviation of post-treatment SNOT-22 scores in the two groups. The non-inferiority margin was 9 units on the SNOT-22.

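### The achieved power for non-inferiority uses the SD of post-treatment SNOT-22 scores although the endpoint is change from baseline, and no stated analysis tests the 9-unit margin

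*SAP*

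**What the plan says.** All the relevant analysis text is in the three paragraphs of the SAP.

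- Paragraph 1 sets the endpoint: "The primary endpoint was the overall change in SNOT-22 scores from baseline to the final study visit".
- Paragraph 2 analyses it with a "repeated-measures analysis of variance (ANOVA) to assess for a group x time interaction on clinical scores". Covariate adjustment comes only afterwards: "For the secondary analysis of the primary outcome, this model was modified to include baseline clinical covariates".
- Paragraph 3 reports an achieved power for non-inferiority, obtained by the method of the prospective calculation with two inputs updated: "the achieved power was based on the actual number of randomized subjects and the actual pooled standard deviation of post-treatment SNOT-22 scores". It then adds: "The non-inferiority margin was 9 units on the SNOT-22".

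In the Protocol, the opening background answer presents the study as one that would show antibiotics are unnecessary after this surgery. The answer to question 36 makes the hoped-for change in prescribing conditional: "if this study shows that the outcomes of patients undergoing sinus surgery without antibiotics are not worse". The answer to question 39 allows withdrawal: "If the patient does not want to participate further then they may opt out at any time during the study".

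**The concern.** The power figure and the endpoint are on different scales of variability. The SD of final scores governs an unadjusted comparison of final scores, an analysis the SAP does not list. The endpoint is change, and the precision of a comparison of changes depends on the SD of change, which also involves the baseline SD and the within-patient correlation. Neither is mentioned.

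Two further points attach to the same paragraph. The calculation counts everyone randomized, whether or not they contribute a final SNOT-22. And the 9-unit margin appears nowhere else in the SAP text. The interaction is a test of difference, and the power figure is not described as using the observed difference between arms.

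At stake is the conclusion that patients do no worse without antibiotics. A reader could take a non-significant interaction and a respectable power figure together as proof of non-inferiority, although neither shows it.

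**Working it through.** **Can the plan's own figure be reproduced?** No. The text gives no achieved power, SD, alpha or number randomized, and the prospective calculation it relies on is not in the supplied documents. What can be checked is whether the stated inputs fit the stated endpoint.

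**Inputs**

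- Margin 9 units: SAP, paragraph 3.
- Planned enrolment 140: Protocol, question 11. Taken as 70 per arm; the 1:1 split is an assumption, and the SAP would use the actual number randomized.
- Assumed: one-sided alpha 0.025, true difference 0, SD 20 at both time points, two time points, and the correlations and missing rates shown below.

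**Formulas**

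- Power = Φ(9 / (SD × √(2/n)) − 1.96), with n per arm.
- For two time points, SD of change = √(SDpre² + SDpost² − 2ρ × SDpre × SDpost).
- Setting this equal to SDpost gives SDpre² = 2ρ × SDpre × SDpost, so ρ = SDpre/(2 × SDpost). For SDpre/SDpost of 20/20, 20/15 and 20/25 the break-even correlation is 0.50, 0.67 and 0.40.

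With two time points the group-by-time test is the two-sample test on change scores, so this SD governs it. With more visits the interaction depends on the whole within-patient covariance, and neither SD gives its exact power.

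**Step 1: SD of final scores against SD of change (n = 70 per arm)**

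| SD used | Value | SE = SD × √(2/70) | Power |
|---|---|---|---|
| Post-treatment (SAP method) | 20.00 | 3.38 | 75.9% |
| Change, ρ = 0.3 | 23.66 | 4.00 | 61.4% |
| Change, ρ = 0.5 | 20.00 | 3.38 | 75.9% |
| Change, ρ = 0.7 | 15.49 | 2.62 | 93.0% |

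For example, in the first row 9/3.38 = 2.66, 2.66 − 1.96 = 0.70, and Φ(0.70) ≈ 0.76.

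The pattern persists under other assumptions:

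| Assumptions | SAP method | Change, ρ = 0.3 | Change, ρ = 0.7 |
|---|---|---|---|
| Both SDs 15, one-sided 0.025 | 94.4% | 85.1% | 99.6% |
| Both SDs 25, one-sided 0.025 | 56.7% | 43.6% | 78.5% |
| Both SDs 20, one-sided 0.05 | 84.6% | 72.7% | 96.3% |
| SDpre 25, SDpost 20, one-sided 0.025 | 75.9% | 50.7% | 84.0% |

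**Step 2: number randomized against number analysed (SD 20)**

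- Nobody missing, 70 per arm: 75.9%.
- 10% without a final score, 63 per arm: 71.4%.
- 20% without a final score, 56 per arm: 66.3%.

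**Step 3: does any stated result test the margin?** Take the case most favourable to the SAP, where the SD of change is also 20.

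- SE = 20 × √(2/70) = 3.38; t(138) = 1.977; 95% CI half-width = 6.68.
- An observed disadvantage for placebo below 6.68 is non-significant. The upper limit reaches 9 once the disadvantage is 9 − 6.68 = 2.32 or more.
- So any observed disadvantage from about 2.3 to 6.7 units is non-significant without showing non-inferiority. At 4.5 the interval is 4.5 ± 6.68, or −2.2 to 11.2, with p = 0.19.
- The power figure stays at 76% throughout, because it does not move with the observed difference.

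**The case against.** The strongest reply has four parts.

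**The prospective calculation is unseen.** It may have stated the alpha, the quantity compared and even a decision rule. This stands as a limit: the missing alpha and calculation are not counted as errors, and the statement that nothing tests the margin applies to the supplied text. It does not remove the mismatch, because the SD and the N used are stated in the SAP itself.

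**The SAP never claims this is the power of the interaction test.** That is true. But a margin test on the stated endpoint also depends on the SD of change, so the input is wrong for either reading.

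**Under randomization, final scores and changes have the same expected difference between arms, and the SD of final scores may be conservative.** The first half is right but concerns the target, not the variance, and power depends on variance. The second half holds only above the break-even correlation, or for a model adjusted for baseline SNOT-22. The primary model is not described as adjusted. The ANCOVA is secondary, and the baseline factors the SAP names are culture result, prior surgery, asthma and polyps.

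**The N point is hypothetical.** Largely so. No document reports a missing final score, and question 37 of the Protocol lets subjects withdraw before randomization, which would already keep them out of the count. The point is conditional and secondary.

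It is also fair that the answer to question 36 is a conditional risk-benefit remark rather than a formal objective. The background answer is the better evidence of intent, and it points the same way.

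**Conclusion.** The concern holds. The achieved-power calculation takes its SD from a different analysis than the one the SAP specifies for its primary endpoint. The figure may be too high or too low, and the documents do not allow the direction or size to be fixed. Under the illustrative assumptions, the SAP's 76% compares with 61% to 93% for correlations of 0.3 to 0.7. That range shows sensitivity and is not an estimate of the error in this trial. Using the number randomized adds overstatement only to the extent that final scores are missing.

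The more consequential part is the margin. In the supplied text it is linked to no inferential result, so following the SAP as written yields no valid test of non-inferiority, even if the SD were right. This should be fixed. No stated number is claimed to be wrong.

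**What to change.** State a decision rule, for example: non-inferiority of placebo is concluded if the two-sided 95% confidence interval for the between-arm difference in mean SNOT-22 change, baseline to last visit, excludes a 9-unit disadvantage for placebo. If the prospective calculation used another level, use that level.

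If a power or precision figure is kept, compute it from the SD the analysis uses (SD of change, or model residual SD) and the number of subjects analysed, and label it supplementary.

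The SAP is written in the past tense, so if this rule was not prespecified, report it as a change made after the original analysis.

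The cost is SAP wording and one recalculation from data already collected. The quoted power may become less favourable, and the interval may not exclude 9 units.

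### Achieved non-inferiority power counts every randomized subject, though a subject without a final SNOT-22 score adds little or nothing to the primary comparison

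*SAP*

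**What the plan says.** The SAP's final paragraph describes a power figure computed after the fact: "The achieved power for non-inferiority was calculated via the same methods as the prospective power analysis". It then names two replacement inputs, one for the sample size and one for the spread: "the achieved power was based on the actual number of randomized subjects and the actual pooled standard deviation of post-treatment SNOT-22 scores". The margin is fixed: "The non-inferiority margin was 9 units on the SNOT-22".

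The first paragraph of the SAP defines the outcome that this power is meant to describe: "The primary endpoint was the overall change in SNOT-22 scores from baseline to the final study visit". The second says that the primary and secondary outcomes were "analyzed using a repeated-measures analysis of variance (ANOVA) to assess for a group x time interaction on clinical scores". The available text names no analysis set and no rule for missing scores.

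The protocol allows loss after randomization. Under question 39: "If the patient does not want to participate further then they may opt out at any time during the study". The answer to question 15 says the same about withdrawal. Question 37 describes a separate chance to decline randomization on the day of surgery; those subjects are never in the randomized count and play no part in this point.

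**The concern.** The two inputs describe different sets of people as soon as one randomized subject fails to return. The SD is estimated from those with a post-treatment score. The N includes those without one.

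The endpoint is a within-subject change, so a subject with only a baseline score has no observed value of it. A classical repeated-measures ANOVA needs complete records and would normally drop that subject. Even a likelihood-based model would draw little information on the treatment difference in change from a baseline score alone. Counting the subject in full credits the trial with information it does not have.

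Achieved power is the only non-inferiority statistic that the SAP describes. A reader asking whether the trial could have excluded a 9-unit disadvantage is given this number, and its N does not respond to attrition. For the same SD, a trial with heavy loss would report the same power as one with complete follow-up.

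**Working it through.** The documents give no power value, SD, alpha or count of subjects randomized, so there is no stated figure to reproduce. The check shows how far the choice of N moves the result.

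**Inputs from the documents**
- Margin: 9 units (SAP, last paragraph).
- Planned enrolment: 140 (protocol, question 11). This is a planned total, standing in for the unreported number randomized.

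**Assumptions**
- Equal allocation, so 140/2 = 70 per arm.
- True difference 0.
- SD 20, with 15 to 25 as the range.
- One-sided alpha 2.5%, with 5% as a sensitivity case.
- Loss before the final visit of 0 to 30%, equal in both arms.

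**Formula**

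Power = Φ( 9 / (SD × √(2/n)) − z ), where n is the number per arm and z = 1.96 (one-sided 2.5%) or 1.645 (one-sided 5%).

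**SD 20, one-sided 2.5%**
- No loss, n = 70: 9/(20 × √(2/70)) = 9/3.381 = 2.662; 2.662 − 1.960 = 0.702; power 75.9%.
- 10% loss, n = 63: 9/3.563 = 2.526; minus 1.960 = 0.566; power 71.4%.
- 20% loss, n = 56: 9/3.780 = 2.381; minus 1.960 = 0.421; power 66.3%.
- 30% loss, n = 49: 9/4.041 = 2.227; minus 1.960 = 0.267; power 60.5%.

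With the SD held at 20, the SAP's rule returns 75.9% in all four cases.

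**Other assumptions**

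| SD | One-sided alpha | On number randomized | 10% loss | 20% loss | 30% loss |
|---|---|---|---|---|---|
| 15 | 2.5% | 94.4% | 92.0% | 88.8% | 84.4% |
| 18 | 2.5% | 84.1% | 80.1% | 75.4% | 69.7% |
| 20 | 2.5% | 75.9% | 71.4% | 66.3% | 60.5% |
| 25 | 2.5% | 56.7% | 52.4% | 47.8% | 42.9% |
| 20 | 5% | 84.6% | 81.1% | 76.9% | 72.0% |

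At one-sided 2.5% the overstatement is about 2 to 5 points at 10% loss, 6 to 10 at 20%, and 10 to 15 at 30%. Losing a single subject of 140 (70 against 69) costs about 0.1 to 0.3 points.

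**Does the direction survive if the SD is also questioned?**

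The SAP's SD is that of post-treatment scores, while the endpoint is a change. If baseline and final SDs are both 20 with correlation ρ, the SD of change is 20 × √(2(1 − ρ)). With 20% loss (n = 56), power for the change score at one-sided 2.5% is:
- ρ = 0.2: SD 25.3, power 46.9%
- ρ = 0.5: SD 20.0, power 66.3%
- ρ = 0.6: SD 17.9, power 75.9%
- ρ = 0.7: SD 15.5, power 86.7%

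The rule's 75.9% is too high below a correlation of about 0.6, matches at 0.6, and is too low above it. The effect of N is certain only with the SD held fixed.

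**The case against.** The strongest reply has four parts.

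First, a reader might infer that the SAP restricts the primary analysis to subjects with a final-visit score. It does not say so. That restriction is inferred from the endpoint and the usual behaviour of repeated-measures ANOVA. This stands as a limit on the claim. It does not remove the mismatch, because the SD still comes only from subjects with post-treatment scores, and a baseline-only subject is worth much less than a full one under any standard model.

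Second, a reader might infer that the reported power is too high whenever anyone withdraws. That is too broad. Someone who declines before randomization is not counted. Someone who stops the study drug but completes the final questionnaire costs nothing. One lost subject barely moves the figure. And as shown above, the separate SD question can offset or enlarge the error, so the net direction against the power of the primary comparison is undetermined. A possible offset from another input does not justify the wrong N.

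Third, no document reports any loss, and the size rests almost wholly on assumed values. That is so. Nor is the SAP's rule strictly constant under attrition, since the observed SD may shift with who remains; the illustration holds it fixed to isolate the N.

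Fourth, achieved power is a descriptive figure, and changing its N alters no estimate, interval or test. This is true, and it limits the consequence. But no other non-inferiority statistic is described, so the figure carries more weight than it ordinarily would.

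**Conclusion.** The point holds in a conditional form. The SAP states a rule that pairs the number randomized with an SD from subjects who have post-treatment scores, and nothing in the available text reconciles them. For fixed SD, margin and alpha, the resulting power is overstated to the extent that randomized subjects lack a final score.

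Under the central assumptions, 20% loss means quoting 75.9% where the analysed number supports 66.3%, a gap of 9.6 points. With no loss the gap is zero. The actual overstatement cannot be computed, because neither the loss nor the power is given.

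The finding does not establish that the reported figure misses the power of the primary comparison in a known direction, because that also depends on the SD. The prospective power analysis that the SAP refers to is not in the available text, and its absence is not held against the plan.

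**What to change.** In the last paragraph of the SAP, replace the count of randomized subjects with *the actual number of subjects per arm contributing to the primary SNOT-22 analysis*. Beside the power figure, report the number randomized and the number analysed in each arm, so that a reader can see whether the two differ.

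The cost is one phrase and one recalculation. The stated power may become less favourable. If no randomized subject was lost, the figure is unchanged and the counts show why.

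This change settles the N only. Whether a post-treatment SD is right for a change endpoint needs its own answer.

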RESPONSE: Functional endoscopic sinus surgery (FESS) is a commonly performed procedure in the United States to treat chronic rhinosinusitis. Common practice is to prescribe prophylactic antibiotics postoperatively. This is similar to the long tradition of prophylactic antibiotics after tonsillectomy. The American Academy of Otolaryngology - Head and Neck Surgery recently strongly recommended against prophylactic antibiotics after tonsillectomy. In this light, this study would demonstrate the lack of need for antibiotics after FESS. Currently [name] does not prescribe antibiotics except when evidence of active infection was found during surgery. [name] currently prescribes antibiotics. This study would prospectively compare the two groups in a randomized fashion. Two previous studies have been performed (Jiang et al. Postoperative antibiotic care after functional endoscopic sinus surgery. *Am J Rhinol* 22, 608-612, 2008); (Albu, et al. Prophylactic antibiotics in endoscopic sinus surgery: A short follow-up study. *Am J Rhinol* 24 306-309, 2010.) These studies were both randomized, placebo controlled prospective studies. Albu et al found that amoxicillin/clavulanate improved the outcome in the "early blood crust healing" and the endoscopic score was improved. Jiang et al. showed that amoxicillin/clavulanate did not improve short term outcomes of FESS. Both studies were limited by a lack

of a prospective instrument to evaluate symptoms. We plan to use the Sinonasal outcomes test -22 (SNOT-22), which is a validated quality of life instrument in sinusitis.

4) What is the estimated completion date? (MM/YYYY)

RESPONSE: 06/2015

5) Who specifically (name, title, and department) is going to perform the coordinator function? Discuss his/her relevant qualifications (training, education, experience):

The PI, [name], has assumed coordinator function. He has had experience and training through the Harvard Catalyst education offerings in clinical studies.

6a) Who is going to supervise the study coordinator(s)? When applicable, indicate if support and oversight will be provided by the Ophthalmology Clinical Research Office (OCRO).

6b) Describe the PI's plan to provide adequate training, and supervision (e.g., regular meetings, training opportunities):

[name] will be supervising all aspects of the study and meets regularly (weekly) with [name] on matters of enrollment, patient compliance, and monitoring of adverse events.

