A moderate rise in AST (SGOT) and/or ALT (SGPT) has been noted in patients treated with ampicillin-class antibiotics but the significance of these findings is unknown. Hepatic dysfunction, including increases in serum transaminases (AST and/or ALT), serum bilirubin, and/or alkaline phosphatase, has been infrequently reported with Augmentin. It has been reported more commonly in the elderly, in males, or in patients on prolonged treatment. The histologic findings on liver biopsy have consisted of predominantly cholestatic, hepatocellular, or mixed cholestatic-hepatocellular changes. The onset of signs/symptoms of hepatic dysfunction may occur during or several weeks after therapy has been discontinued. The hepatic dysfunction, which may be severe, is usually reversible. On rare occasions, deaths have been reported (less than 1 death reported per estimated 4 million prescriptions worldwide). These have generally been cases associated with serious underlying diseases or concomitant medications.

Renal

Interstitial nephritis and hematuria have been reported rarely. Crystalluria has also been reported

Hemic and Lymphatic Systems

Anemia, including hemolytic anemia, thrombocytopenia, thrombocytopenic purpura, eosinophilia, leukopenia, and agranulocytosis have been reported during therapy with penicillins. These reactions are usually reversible on discontinuation of therapy and are believed to be hypersensitivity phenomena. A slight thrombocytosis was noted in less than 1% of the patients treated with Augmentin. There have been reports of increased prothrombin time in patients receiving Augmentin and anticoagulant therapy concomitantly.

Central Nervous System

Agitation, anxiety, behavioral changes, confusion, convulsions, dizziness, insomnia, and reversible hyperactivity have been reported rarely.

Miscellaneous

Tooth discoloration (brown, yellow, or gray staining) has been rarely reported. Most reports occurred in pediatric patients. Discoloration was reduced or eliminated with brushing or dental cleaning in most cases.

2. Placebo Arm:

The main theoretical risk from not giving antibiotics post operatively would be a risk of postoperative infection. This would manifest as sinusitis-like symptoms. Worst case scenario would result in complications of sinusitis (orbital infection, meningitis, brain abscess). These complications are rare, and [name] has not experienced them while not giving routine postoperative antibiotics as is his usual practice.

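### Meeting the 9-unit SNOT-22 margin does not exclude a moderate excess of post-operative infection, so it cannot by itself support a conclusion that antibiotics are not needed

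*SAP*

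**What the plan says.** The background response in the Protocol (before question 4) states the aim: "this study would demonstrate the lack of need for antibiotics after FESS". Question 35 gives the intended consequence: "Hopefully surgeons would stop giving postoperative antibiotics". Question 36 makes the hoped-for fall in prescribing conditional on outcomes without antibiotics being no worse.

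Question 27, under the placebo arm, names the harm: "The main theoretical risk from not giving antibiotics post operatively would be a risk of postoperative infection". It adds: "This would manifest as sinusitis-like symptoms". Question 32 schedules an endoscopic check one week after surgery, partly to look for infection.

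In the SAP, the first paragraph defines the primary outcome: "The primary endpoint was the overall change in SNOT-22 scores from baseline to the final study visit". The secondary outcomes are the change in endoscopic score, "as well as rates of post-operative infection". The second paragraph names one type of model, a repeated-measures ANOVA "to assess for a group x time interaction on clinical scores", with a covariate-adjusted version for the primary outcome. The third paragraph gives the only limit: "The non-inferiority margin was 9 units on the SNOT-22". No acceptable excess and no method for a proportion is given for infection.

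**The concern.** The intended conclusion is wider than the criterion, and the gap falls on the harm that the protocol itself puts first. Infection affects a minority of subjects. Its effect on a group mean is the excess proportion infected multiplied by the extra SNOT-22 units that each infected subject still carries at the final visit. If infections are over by then, the second factor is near zero and the primary endpoint does not register them.

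The secondary infection comparison does not close the gap at this sample size, because a non-significant difference does not show that a moderate excess is absent. A report could therefore pair SNOT-22 non-inferiority with no significant difference in infection and conclude that antibiotics are unnecessary, while infection was in truth appreciably more frequent on placebo. Since the stated hope is to change prescribing, that inference matters.

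**Working it through.** **Inputs from the documents.** Margin of 9 SNOT-22 units (SAP, third paragraph); 140 subjects in total (Protocol, question 11).

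**Inputs assumed, because the visible text does not give them.** Allocation 1:1, so 70 per arm; non-inferiority judged by a confidence limit at one-sided 2.5%; power of 80% or 90% at zero true difference; true infection rates; and *d*, the SNOT-22 worsening per infected subject at the final visit.

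There is no stated power figure to reproduce. The SAP refers to a prospective power analysis that is not in the text supplied.

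**1. Dilution in the true mean.** Shift = *e* × *d*, where *e* is the excess proportion infected. The shift reaches 9 when *e* = 9/*d*:
- *d* = 18: 9/18 = 50 points
- *d* = 27: 9/27 = 33 points
- *d* = 45: 9/45 = 20 points
- *d* = 0: never

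**2. The test is stricter than the true mean.** SE = 9/(1.960 + z), with z for the assumed power:
- 80% power: 9/(1.960 + 0.842) = 3.21, which implies SD = 3.21 × √35 = 19.0
- 90% power: 9/(1.960 + 1.282) = 2.78, which implies SD = 16.4

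The margin is met only if the observed difference is below 9 − 1.960 × SE, that is 2.70 or 3.56 units. At *d* = 18 these correspond to an excess of about 15 points (2.70/18) or 20 points (3.56/18), not 50. With true infection of 5% versus 55% and *d* = 18, the margin is met in only about 2.5% of trials.

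**3. Chance of meeting the margin at a 10-point excess (5% versus 15%).**
- *d* = 0: 80% or 90%, the assumed power.
- *d* = 18: the shift is 0.10 × 18 = 1.8. The simple formula Φ((9 − 1.8)/SE − 1.960) gives 61% or 74%. Enumerating the infection counts and allowing for the variance they add gives 58% or 69%.

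**4. Chance that the margin is met and Fisher's exact test on infection is also non-significant (two-sided 5%).** The SAP names no test; Fisher is an illustration.

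| True infection, antibiotic vs placebo | *d* (units) | Joint probability at 80% / 90% power |
|---|---|---|
| 5% vs 15% | 0 | 47% / 53% |
| 5% vs 15% | 9 | 44% / 50% |
| 5% vs 15% | 18 | 38% / 45% |
| 5% vs 15% | 27 | 32% / 39% |
| 5% vs 20% | 0 to 18 | 17% to 25% |
| 5% vs 25% | 0 to 18 | 5% to 8% |

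The power of Fisher's test alone is 41% at 5% versus 15% (52% for a pooled z-test), 72% at 5% versus 20%, and 91% at 5% versus 25%. Holding the excess at 10 points and moving the antibiotic-arm rate from 2% to 10%, with *d* from 0 to 18, gives a joint probability of 32% to 62%.

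**5. What an infection interval would look like.** Suppose 4 of 70 in each arm are infected. The Wilson limits for 4/70 = 0.0571 are 0.0224 and 0.1379. The Newcombe half-width is √[(0.0571 − 0.0224)² + (0.1379 − 0.0571)²] = 0.088. Even with identical counts, an excess of up to 8.8 points is not ruled out.

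**The case against.** **SNOT-22 and endoscopy would detect infection.** In part. The protocol expects infection to show as sinusitis-like symptoms, so persisting infection does lower the chance of meeting the margin (step 3). The one-week endoscopy and the endoscopic score are further chances to see it. None of these sets an infection excess to be ruled out.

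**A reader might infer that even a large excess of infection would slip through.** The documents and the arithmetic do not support that. The 50, 33 and 20 points in step 1 concern the true mean; a confidence-limit test fails much earlier. An ordinary comparison of the infection rates already listed as an outcome would usually expose a 20-point excess. This objection stands, and it confines the point to moderate excesses.

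**A reader might infer that the plan intends to combine the two results into a finding of no need.** No such decision rule is written. The statement of aim is background text in an ethics form, and question 36 is a conditional hope. The risk lies in how the result is reported.

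**A reader might infer that infection was never defined or given a limit.** Pages were removed and the prospective power analysis is not in the supplied text, so that cannot be established.

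**Most numerical inputs are assumed.** True. The percentages illustrate a scenario and do not measure this trial. The dilution result in step 1 needs only the margin and a value for *d*.

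**Conclusion.** The point holds for a moderate excess of infection. Non-inferiority within 9 SNOT-22 units is a statement about mean symptoms at the final visit. It does not carry over to infection, and neither does a non-significant comparison of infection rates at about 70 per arm.

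On the assumptions listed, a true tripling of infection from 5% to 15% would pass both readings in roughly four to five trials in ten when each infection costs 0 to 18 units at the final visit, and in about a third at 27 units. The figure falls quickly as the excess grows. Confidence in its exact size is limited, because SD, alpha, power, allocation, infection rates and *d* are all assumed.

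The SNOT-22 analysis itself is not put in question here. What does not follow is the wider conclusion about need.

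**What to change.** - Word the non-inferiority conclusion as applying to SNOT-22 symptoms only. Do not draw a conclusion of no need for antibiotics from the 9-unit margin, or from a non-significant infection comparison.
- Analyse infection as a proportion: counts by arm, and the placebo minus antibiotic risk difference with a 95% confidence interval (for example Newcombe). Quote the upper limit as the excess that the trial did not rule out.
- If an acceptable excess was fixed before unblinding, state it and judge the upper limit against it. If none was fixed, label the infection result descriptive and do not set a limit afterwards.

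The cost is a few lines in the SAP and the conclusion, and one table row; no further subjects are needed. The downside is a narrower headline: with about 70 per arm the infection interval will probably be too wide to support a claim of no need, so the claim may have to stay with symptoms.
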